6.9.2 Storage

Prior to dispensing, Nucala will be stored in a refrigerator, below 25°C (77°F) in the original carton and protected from light. Prior to SQ administration, Nucala will be reconstituted with 1.2 mL Sterile Water for Injection, USP.

6.9.3 Dispensing of Study Drug

Regular study drug reconciliation will be performed to document drug assigned, drug dispensed, drug returns, and drug remaining. This reconciliation will be logged on the drug reconciliation

form, and signed and dated by the study team. Drug dispensation will occur at scheduled follow-up visits.

6.9.4 Return or Destruction of Study Drug

At the completion of the study, there will be a final reconciliation of drug shipped, drug dispensed, drug returns, and drug remaining. This reconciliation will be logged on the drug reconciliation form, signed and dated. Any discrepancies noted will be documented and investigated, prior to return or destruction of unused study drug. Remaining drug will be destroyed on site will be documented in the study files.

7 Study Procedures

7.1 Visit 1 (Week -2/Screening & Enrollment)

- a) Informed Consent
- b) History & Physical
- c) 4 mm punch skin biopsy (**4 mm punch skin biopsy within 6 months prior to visit 1 is acceptable**)
- d) UCT score assessment
- e) Review and distribute UAS log book
- f) Blood work: CBC with differential, serum IgE level, chronic urticaria index, IgE Fc receptor antibody functional assay (**Blood work within 6 months prior to visit 1 is acceptable**)
- g) Urine Pregnancy Test (if applicable)
- h) Photograph Biopsy site (**Photograph Biopsy site within 6 months prior to visit 1 is acceptable**)
- i) Dispense cetirizine (Zyrtec) 10 mg PO BID (#140 tablets)

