1.6 Risks and Benefits

The postulated benefits of Nucala include sustained immunomodulatory effects resulting in improvement of pruritus and clearance of lesional skin without the direct end organ toxicities seen

The following risks of Nucala are felt to be low and manageable with the study protocol and do not outweigh the aforementioned benefits:

1. Hypersensitivity Reactions

Anaphylaxis has occurred following administration of Nucala. This risk is idiosyncratic and will be minimized by administrating Nucala in a supervised medical setting and requiring study participants to carry epinephrine autoinjectors at all times.

2. Acute Asthma Symptoms or Deteriorating Disease

Nucala is not indicated for the treatment of acute asthma symptoms or acute exacerbations. This risk will be minimized by screening all study participants with asthma via the asthma control test (ACT) questionnaire and peak flow measures at each visit. Those with ACT scores less than 20 and/or peak flow measures greater than 10% below their personal best will not receive the study drug on the day of their visit. Subjects with severe asthma (requiring high-dose inhaled or systemic corticosteroids) will be excluded from the study.

3. Opportunistic Infections: Herpes Zoster

In controlled clinical trials, two serious adverse reactions of herpes zoster occurred in subjects treated with Nucala compared with none in placebo. The mechanism by which this adverse reaction occurs is unclear. Subjects will be monitored for signs and symptoms of shingles and treated should shingles develop.

4. Reduction of Corticosteroid Dosage

Reductions in corticosteroid dose, if appropriate, will be gradual and performed under the direct supervision of a physician.

5. Parasitic (Helminth) Infection

Eosinophils may be involved in the immunological response to some helminth infections. Patients with known parasitic infections were excluded from participation in clinical trials. It is unknown if Nucala will influence a patient's response against parasitic infections. This risk will be minimized by excluding enrollment of study participants with known tapeworm or roundworm infections.

2 Study Objectives

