3.1 General Description

This is an open-label, single arm exploratory study of mepolizumab in the treatment of CSU. The primary endpoint will be the mean reduction in the seven day urticaria activity score (UAS7) before and after 10 weeks of treatment with mepolizumab. Secondary endpoints will be the mean

reduction of the urticaria control test (UCT) score and the weekly itch severity score (ISS) before and after treatment. Enrollment examination will include a standardized history and examination, baseline UCT score, CBC with differential, serum IgE level, chronic urticaria index, IgE Fc receptor antibody functional assay, and a 4 mm punch biopsy of lesional skin. Patients will discontinue all anti-histamines and start cetirizine 10 mg PO BID which will be continued throughout the study duration. Patients will be provided with a log book to track daily urticaria signs and symptoms in a standardized manner for UAS scoring. At week 0 (enrollment visit +7 days), baseline UAS7 and ISS score will be assessed and skin biopsy results reviewed. Patients with a confirmatory skin biopsy will receive 200 mg SC of mepolizumab at week 0,2,4,6, and 8. UAS-7 and weekly ISS score will be calculated at week 0, 4, 8, and 10. UCT scoring will be calculated at week 0 and at week 10. Repeat CBC with differential, serum IgE level, and measures of basophil serum activation (chronic urticaria index, IgE FC Receptor antibody functional assay) will be assessed at week 10. Attached to this document is a protocol summary.

4 Number of Subjects

Twenty

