5.2 Exclusion Criteria

Patients are to be excluded based on the following criteria:

- Vulnerable study population
- If you are female and pregnant
- Biopsy proven neutrophilic rich urticarial which is unlikely to respond to mepolizumab given the postulated therapeutic mechanism
- Known history of adverse reaction to mepolizumab (Nucala)

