5.3 Subject Recruitment, Enrollment and Screening

Subjects will be enrolled from the Departments of Allergy and Dermatology at the Mayo Clinic in Florida. The study has an accrual target of 20 patients. In the year 2014, 188 unique patients with CSU were evaluated in the Dermatology and Allergy outpatient clinics at Mayo Clinic in Florida and thus no difficulties in accrual based on historical volumes are anticipated. Co-departmental participation aids in reaching accrual targets and minimizing referral bias. The accrual period will last 10 months. Patients will be provided with a Research Participant Consent and Privacy Authorization Form describing the study drug, protocol, inclusion and exclusion criteria, as well as risks and benefits of participation.

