6.6 Prior and Concomitant Therapy

Study participants will stop other first-generation antihistamines and start cetirizine (Zyrtec) 10 mg 1 tablet bid two weeks prior to the first dose of Nucala, and continue throughout the duration of the study.

Epinephrine auto-injectors will be dispensed to the participants on baseline visit and must be carried at all times.

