7.2 Visit 2 (Week 0± 5 days Baseline)

- a) UAS7 score assessment
- b) ISS score assessment
- c) Nucala 200mg injection
- d) Dispense epinephrine auto-injector

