9.1 Definitions

Unanticipated Problems Involving Risk to Subjects or Others (UPIRTSO)

Any unanticipated problem or adverse event that meets the following three criteria:

- Serious: Serious problems or events that results in significant harm, (which may be physical, psychological, financial, social, economic, or legal) or increased risk for the subject or others (including individuals who are not research subjects). These include: (1) death; (2) life threatening adverse experience; (3) hospitalization - inpatient, new, or prolonged; (4) disability/incapacity - persistent or significant; (5) birth defect/anomaly; (6) breach of confidentiality and (7) other problems, events, or new information (i.e. publications, DSMB reports, interim findings, product labeling change) that in the opinion of the local investigator may adversely affect the rights, safety, or welfare of the subjects or others, or substantially compromise the research data, **AND**
- Unanticipated: (i.e. unexpected) problems or events are those that are not already described as potential risks in the protocol, consent document, not listed in the Investigator's Brochure, or not part of an underlying disease. A problem or event is "unanticipated" when it was unforeseeable at the time of its occurrence. A problem or event is "unanticipated" when it occurs at an increased frequency or at an increased severity than expected, **AND**
- Related: A problem or event is "related" if it is possibly related to the research procedures.

Adverse Event

An untoward or undesirable experience associated with the use of Nucala in a research subject. Initial screening for AE will include non-directed questioning of the patient at each follow-up visit during the study period.

Serious Adverse Event

Adverse events defined as serious will the following:

- death
- life threatening adverse experience
- hospitalization
- inpatient, new, or prolonged; disability/incapacity
- persistent or significant disability or incapacity

- birth defect/anomaly

and any problems/events that in the opinion of the sponsor-investigator may have adversely affected the rights, safety, or welfare of the subjects or others, or substantially compromised the research data.

All adverse events that do not meet any of the criteria for serious, will be regarded as **non-serious adverse events** as previously defined above.

Adverse Event Reporting Period

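### The only scheduled pregnancy test falls nominally 14 days before the first injection, so a pregnancy still unrecognised at Visit 2 could be dosed under the schedule as written

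*Combined protocol and SAP*

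**What the plan says.** All references are to the combined protocol and SAP.

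- **Exclusion.** Section 5.2 lists "If you are female and pregnant" among the exclusions and sets no date at which that status must be confirmed.
- **Test.** Section 7.1 (Visit 1, Week -2) has item g, "Urine Pregnancy Test (if applicable". The schedule table agrees: the Urine HCG row has one mark, under Week -2.
- **First dose.** Section 7.2, headed "Visit 2 (Week 0± 5 days Baseline", lists four items: the UAS7 score, the ISS score, the first 200 mg injection and the epinephrine auto-injector. There is no pregnancy test. Visits 3 to 7 list none either.
- **Interval.** Section 6.6 starts cetirizine "two weeks prior to the first dose of Nucala", and section 7.1 has it dispensed at Visit 1. Section 3.1 places baseline differently: "At week 0 (enrollment visit +7 days".
- **Conditions for dosing.** The one condition that section 3.1 attaches to dosing at week 0 is a confirmatory biopsy. Section 1.6 adds a same-day hold for participants with asthma who fail a control check; they "will not receive the study drug on the day of their visit".

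**The concern.** An exclusion for pregnancy is meant to keep the study drug from pregnant women, so the time that matters most is when exposure begins. Here the status is tested once, at enrollment, and not again before the first injection. The visible eligibility criteria contain no contraception requirement, and the visible text has no pregnancy check tied to the first dose.

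What is at stake is participant safety: a first injection given to someone the plan intends to exclude. Section 9.1 includes "birth defect/anomaly" among its criteria for a serious event. Efficacy results are not at stake, because the UAS7 endpoint, the sample size and the paired t-test do not depend on this.

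**Working it through.** The plan states no figure for the gap between test and first dose, so there is nothing to reproduce. The check is a count, a date calculation and a walk through the possible cases.

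**Inputs**

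- Visit 1: Week -2, no window stated (section 7.1). I assume it falls on day -14.
- Visit 2, first injection: day 0, window ±5 days (section 7.2).
- Cetirizine lead-in: two weeks before the first dose (section 6.6), with tablets dispensed at Visit 1 (section 7.1, item i).
- Alternative timing: week 0 is 7 days after enrollment, no window stated (section 3.1).
- Accrual target: 20 (sections 4 and 5.3). Withdrawn subjects may be replaced (section 5.4.1).

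**Step 1: count the scheduled tests.** Visit 1 has one and Visits 2 to 7 have none, so 1 of 7 visits has a test. The visit lists and the schedule table agree on this, so it is unlikely to come from a broken table.

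**Step 2: gap from test to first dose** = day of Visit 2 minus day of Visit 1.

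- Nominal: 0 - (-14) = 14 days.
- Latest Visit 2: 5 - (-14) = 19 days.
- Earliest Visit 2: -5 - (-14) = 9 days by arithmetic. This is shorter than 14, so it would breach the lead-in in section 6.6.
- Under section 3.1: 7 days, which conflicts with section 6.6 for the same reason.

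On every reading, no test is scheduled on the day of the first injection.

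**Step 3: who could be dosed while pregnant?**

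| Situation at Visit 2 | What the plan does now | What a Visit 2 test adds |
|---|---|---|
| Pregnancy detectable at Visit 1 | Caught by the Visit 1 test | Nothing |
| Pregnancy known or reported by Visit 2 | Actionable under 5.2 and 5.4.1 | Nothing |
| Present at Visit 1, too early to detect, still unrecognised | No check before dosing | A second look, nominally 14 days later |
| Conceived after Visit 1, unrecognised | No check before dosing | Uncertain: at most 14 days since conception (19 with the window), and the documents give no detection limit |

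The gap therefore concerns the last two rows, and the added test helps chiefly in the third.

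**Step 4: after the fix.** The last test is on the day of the first injection, a gap of 0 days, and 2 of 7 visits have a test. Extra tests: at most 20 × 1 = 20, plus one per replacement.

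**The case against.** The strongest reply is that the plan is less exposed than its schedule suggests. The exclusion in 5.2 has no expiry, and section 5.4.1 allows discontinuation for an eligibility violation or for any other reason. An investigator who learns of a pregnancy by Visit 2 can act on it. This stands. A reader might infer that any participant who becomes pregnant after Visit 1 would be dosed; the documents do not support that. The point is limited to a pregnancy that nobody has recognised.

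Second, a 0-day calendar gap is not the same as detection. A conception in the preceding two weeks may be missed by the repeat test too. This also stands, and it is why the benefit is claimed mainly for pregnancies too early to detect at Visit 1.

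Third, if 14 untested days matter before dose 1, the same spacing precedes doses 2 to 5. One added test shortens the time from last test to last injection only from 70 days (day -14 to day 56) to 56. That is correct. A reader might infer that testing is needed before every dose. That would need evidence on risk during treatment that the documents do not give, so nothing is claimed about those doses.

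Fourth, the supporting text is thin. The birth-defect item in 9.1 belongs to a general list of serious-event criteria, and pregnancy is not among the risks in 1.6. A reader might infer a recognised fetal risk from mepolizumab; the documents contain no such data. The asthma hold shows only that the protocol already uses same-day checks before dosing.

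Finally, the consent pages are not available. Section 5.3 says the form covers matters "describing the study drug, protocol, inclusion and exclusion criteria", and it may impose contraception or reporting duties. Those could lower the residual risk. They would not add a test to the visit schedule, and they would not detect a pregnancy already present at Visit 1.

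**Conclusion.** The point holds within limits. The exclusion is tested once, nominally 14 days before exposure begins (up to 19 with the Visit 2 window, about 7 under section 3.1). An unrecognised pregnancy at Visit 2 could be dosed by staff following the schedule exactly. The 14 and 19 assume that Visit 1 falls on day -14. A gap below 14 days should not be read as permitted, because it would breach section 6.6.

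No expected number of exposed pregnancies can be given: the documents do not say how many participants the test applies to, nor how sensitive it is. This is a modest, inexpensive safety improvement and not a threat to the trial's conclusions.

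**What to change.** Keep the Visit 1 test. In section 7.2 (Visit 2), add the same urine pregnancy test, with the same if-applicable condition, ahead of the injection. State that the result is read before dosing and that no dose is given if it is positive. Mark Week 0 in the Urine HCG row of the schedule table.

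The cost is one urine test per applicable participant at a visit already planned (at most 20, plus one per replacement) and a short wait for the result. No visit, endpoint, sample size or analysis changes. The remaining limitation is that a very recent conception may still be missed.

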4.5 Identification of Source Data

The following source data will be directly recorded on the Case Report Form (CRF):

- UCT score
- ISS score
- UAS7 score
- Screening and documentation of adverse events
- Confirmation of patient counseling and education

The following source data will not be directly recorded in the CRF, but will be captured in supportive documentation to include study source documents and the EMR:

- Laboratory results and clinical interpretation of the values
- Histopathologic interpretations of skin biopsy tissue. This will include the use of immunohistochemistry to identify IL-5 receptor expression in lesional skin taken prior to treatment.

5 Subject Selection Enrollment and Withdrawal

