5.1 Inclusion Criteria

Informed subject consent will be obtained from those patients meeting the following inclusion criteria:

- Male and female patients 18 years or older.
- Clinical and/or histopathological diagnosis of conventional CSU
- Unresponsive to oral antihistamine therapy
- Good general health as confirmed by medical history
- Patients who are willing and capable of cooperating to the extent and degree required by the protocol; and
- Patients who read and sign an approved informed consent for this study

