6.5 Subject Compliance Monitoring

Study participants will receive Nucala subcutaneous injection at each follow-up visit.

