7.6 Visit 7 (week 10± 5 days)

- a) UAS7 score assessment
- b) ISS score assessment
- c) UCT score assessment
- d) 4mm punch skin biopsy if residual disease
- e) Collect UAS log book
- f) Blood work: CBC with differential, serum IgE level, chronic urticaria index, IgE Fc receptor antibody functional assay
- g) Screen for adverse events
- h) Photograph biopsy site

Week	Wk -2 screen	Wk 0 baseline	Wk 2	Wk 4	Wk 6	Wk 8	Wk 10
Visit	1	2	3	4	5	6	7
Consent/Enroll	X						
Distribute log book	X						
Collect log book							X
Cbc with Diff	X						X
Serum IgE	X						X
CIU index	X						X
IgE Fc Recept Ab	X						X
Urine HCG	X						
UCT		X					X
UAS		X	X	X	X	X	X
ISS		X	X	X	X	X	X
Skin Biopsy	X						X***
Nucala Inj*		X	X	X	X	X	
Cetirizine (Zyrtec) Dispense	X						
Epinephrine auto-injector Dispense		X					
AE Screening**		X	X	X	X	X	X
	
* Nucala Inj = denotes Nucala SQ injection during a visit ** AE Screening = protocol directed screening for adverse events ***At end of study if subjects have residual disease, will biopsy, as necessary, to check for lesional eosinophil tissue density
						

8 Statistical Plan

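### The single dispensing of 140 cetirizine tablets is 28 short, and at nominal timing it covers no day of the week-10 UAS7 diary week

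*Combined protocol and SAP*

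**What the plan says.** Cetirizine is the fixed background treatment. Section 3.1 has patients stop all antihistamines and "start cetirizine 10 mg PO BID which will be continued throughout the study duration". Section 6.6 gives the dose as one 10 mg tablet, "bid two weeks prior to the first dose of Nucala, and continue throughout the duration of the study". Section 4.1 puts participation at twelve weeks, which matches week -2 to week 10.

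The supply is set in Section 7.1, for the week -2 visit: "Dispense cetirizine (Zyrtec) 10 mg PO BID (#140 tablets". The visit lists in Sections 7.2 to 7.6 contain no further cetirizine. In the schedule table after Section 7.6, the row "Cetirizine (Zyrtec) Dispense" is marked only in the week -2 column.

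The primary endpoint (Section 4.2) is the mean UAS7 reduction from before treatment to after 10 weeks of it, and Section 8.1 tests it with a paired t-test. There is no control arm (Section 6.3).

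**The concern.** The tablet count does not match the duration of use that the same document requires, and the missing days fall at the end of the study, where the primary endpoint is read. The before/after contrast assumes the same background antihistamine at both ends. The baseline diary week lies inside the supplied period; the week-10 diary week does not.

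A patient who stopped cetirizine when the tablets ran out would give week-10 UAS7 and itch scores off background therapy. If cetirizine has any effect in that patient, those scores rise and the reduction is understated. In Section 1.5 the authors justify their dosing interval by the wish not to miss a therapeutic effect, so this is the direction they would least want. With no control arm, nothing in the comparison would reveal the change.

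The planned data would not show it either. Section 6.5 on compliance concerns mepolizumab only ("Study participants will receive Nucala subcutaneous injection at each follow-up visit"). The list in Section 4.5 of data entered directly on the CRF has no cetirizine item, and the diary in Section 4.2 scores only wheals and itch.

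**Working it through.** **Inputs.**
- Tablets: 140, dispensed once at week -2 (Section 7.1, schedule table).
- Use: 2 tablets a day (Sections 6.6 and 7.1).
- Start: 14 days before the first dose (Section 6.6, and the week -2 label in 7.1). Section 3.1 instead puts week 0 seven days after enrollment, so a 7-day run-in is checked too.
- End: week 10, day 70, with the first mepolizumab dose as day 0 (Section 7.6).
- Visit windows: ±5 days at Visits 2 to 7 (Sections 7.2 to 7.6).
- Assumption: the diary week for a visit is the seven days before it. The plan sums the score over a week without saying which days. At nominal week 10 this gives days 63 to 69.

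**Where 140 could come from.** 2 × 10 weeks × 7 days = 140. The stated figure equals ten weeks of use with no run-in. That the run-in was left out is an inference; the plan gives no derivation.

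**Nominal timing.** Days supplied = 140 / 2 = 70. Last supplied day = start day + 69. Tablets needed = 2 × (run-in + 70).

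| Run-in | Days of use | Tablets needed | Shortfall | Last supplied day | Days 63–69 unsupplied |
|---|---|---|---|---|---|
| 14 days (6.6, 7.1) | 84 | 168 | 28 tablets, 14 days | -14 + 69 = 55 | 7 of 7 |
| 7 days (3.1) | 77 | 154 | 14 tablets, 7 days | -7 + 69 = 62 | 7 of 7 |

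If the diary week is taken to include the visit day (days 64 to 70), it is still wholly unsupplied in both rows.

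**Visit windows, 14-day run-in.** Suppose cetirizine starts at Visit 1, Visit 2 falls 14 + a days later, and Visit 7 falls 70 + b days after Visit 2, with a and b each from -5 to +5.
- Days of use = 84 + a + b, from 74 to 94, or 148 to 188 tablets. The 140 tablets fall short at every allowed timing.
- The week-10 diary week begins 77 + a + b days after the start. All seven days are unsupplied when 77 + a + b ≥ 70, that is a + b ≥ -7. This holds for 115 of the 121 whole-day combinations.
- For a + b = -8, -9 and -10 (3, 2 and 1 combinations), 6, 5 and 4 of the 7 days are unsupplied.

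If the run-in is instead exactly 14 days before the actual first dose, only b varies. Use is then 84 ± 5 days, or 158 to 178 tablets, and all seven days are unsupplied at every allowed timing.

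**Visit windows, 7-day run-in.** Visit 2 cannot be early, because baseline needs seven diary days (a ≥ 0). The best case is a = 0, b = -5: the diary week is days 58 to 64, supply ends on day 62, and 2 of 7 days are unsupplied. The range is 2 to 7.

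**Week 8.** The nominal diary week is days 49 to 55, fully supplied with either run-in. With the 14-day run-in there is no slack: with c the Visit 6 offset, the week ends 69 + a + c days after the start, so it is fully supplied only when a + c ≤ 0 (66 of 121 combinations).

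**Resupply timing, 14-day run-in.** The latest allowed week-6 visit is 14 + 5 + 42 + 5 = 66 days after the start, with 70 - 66 = 4 days of tablets left. A nominal week-8 visit (day 56) is already the first unsupplied day.

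**The case against.** The strongest reply is that supply is not intake. Sections 3.1 and 6.6 tell patients to keep taking cetirizine, nothing forbids them from obtaining more, and they are seen every two weeks. This stands: the shortfall does not show that anyone stopped. It leaves the plan relying on an unstated step.

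The effect could also be negligible, since an entry criterion is "Unresponsive to oral antihistamine therapy". That stands too. The documents give no figure for the effect of cetirizine on UAS7 in these patients, so no bias or loss of power can be quantified. A bias in this direction would also not create a false positive.

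One could argue that the records are not wholly silent. Section 5.4.1 makes noncompliance with dosing a ground for withdrawal, Section 10.2 names pharmacy dispensing records and diaries as source documents, and the list in Section 4.5 is not said to be the complete CRF. None of these specifies a record of cetirizine intake in the week-10 diary week.

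Section 6.9.3 says that drug is dispensed at follow-up visits, but that section covers the study drug. Cetirizine has its own row in the schedule, with one mark.

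Finally, the figures of 148 to 188 tablets and 115 of 121 assume that Visit 7 is timed from the actual Visit 2, which the protocol does not state, and 115 of 121 is a count of combinations, not a probability. The other anchoring gives a narrower tablet range and leaves the whole diary week unsupplied, so the conclusion does not depend on this choice.

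**Conclusion.** The concern holds. As written, the plan supplies 70 days of cetirizine for 84 days of required use. The shortfall of 28 tablets becomes 14 if the 7-day run-in of Section 3.1 is the intended one. At nominal timing all seven days of the week-10 diary week are unsupplied under either run-in. Across the visit windows, at least 4 of 7 are unsupplied with the 14-day run-in and at least 2 of 7 with the 7-day run-in. The result rests on twice-daily use, a single dispensing, and a diary week that immediately precedes the visit.

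The consequence for the primary result is possible but not established: it needs patients who ran out, did not replace the tablets, and had some benefit from them. The point should be fixed because the error is certain, touches the primary endpoint week and costs very little to remove.

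**What to change.** Reconcile the tablet count in Section 7.1 with Sections 3.1 and 6.6 and the schedule table, and settle whether the run-in is 7 or 14 days. If twice-daily use through week 10 stands with the 14-day run-in, do one of the following:

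- Dispense at least 168 tablets at week -2. A count of 188 covers late visits at both Visit 2 and Visit 7. This is 28 to 48 more tablets per patient.
- Add a cetirizine resupply at week 6 to Section 7 and the schedule table. Week 8 is too late at nominal timing. This is one entry at an existing visit.

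In either case, add one diary item recording cetirizine use in the baseline and week-10 diary weeks.

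If some patients are found to have run out, examine them in a sensitivity analysis and compare baseline with week 8, where Section 3.1 already schedules the score ("UAS-7 and weekly ISS score will be calculated at week 0, 4, 8, and 10"). Because week 8 is fully supplied only when visits do not run late, check each patient's dates first. With adequate supply from the start, this analysis is largely unnecessary.

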4.2 Primary Study Endpoints

The primary endpoint of the study will be the mean UAS7 reduction before and after 10 weeks of treatment with mepolizumab. The urticaria activity score (UAS) is a widely used CSU measure for daily pruritus and number of hives, which summed over a week, gives a UAS7 score. Study participants will document their CSU symptoms using a diary during the 10 week study period using the following daily scoring for a) the number of wheals [none (=0 points), <10 (=1 point), 10–50 (=2 points), or >50 per day (=3 points)], and b) the intensity of pruritus [none (=0 points), mild (=1 point), moderate (=2 points), severe (=3 points)]. The daily UAS score is summed over a week to calculate the UAS7 score (range: 0–42).

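### The 140 cetirizine tablets dispensed at Visit 1 last 70 days of an 84-day course, so at nominal visits and full adherence the week-10 UAS7 week falls outside the supply

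*Combined protocol and SAP*

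**What the plan says.** Section 7.1 gives the only cetirizine quantity in the protocol, at Visit 1 (Week -2): "Dispense cetirizine (Zyrtec) 10 mg PO BID (#140 tablets".

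Two sections set how long it is taken. Section 6.6 prescribes one 10 mg tablet "bid two weeks prior to the first dose of Nucala, and continue throughout the duration of the study". Section 3.1 says: "Patients will discontinue all anti-histamines and start cetirizine 10 mg PO BID which will be continued throughout the study duration". Section 4.1 gives participation as twelve weeks, which agrees with a span from Week -2 to Week 10. Section 3.1 also contains a shorter lead-in: "At week 0 (enrollment visit +7 days), baseline UAS7 and ISS score will be assessed".

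The schedule table at the end of section 7 marks cetirizine dispensing in the Week -2 column only, and the lists for Visits 2 to 7 contain no refill. Section 6.9.3 mentions dispensing at follow-up visits, but under the study-drug heading, so it concerns Nucala.

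On the endpoint, section 4.2 says: "The primary endpoint of the study will be the mean UAS7 reduction before and after 10 weeks of treatment with mepolizumab". It builds the score from the diary: "The daily UAS score is summed over a week to calculate the UAS7 score".

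**The concern.** The plan fixes background cetirizine so that the change in UAS7 can be read against a constant background. There is no control arm (section 6.3), and the analysis is a paired before-and-after test in 20 patients (section 8.1). A change in background treatment between the two measurements would therefore be mixed with the effect of mepolizumab.

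The tablet count does not match the stated duration. A patient who takes every dose has supplied cetirizine throughout the baseline diary week and none left for the week-10 diary week. If such a patient did not obtain more, week-10 scores would most likely rise and improvement would be understated. The week-0 to week-10 change alone would not show this. The week-8 UAS7 is already collected and is a partial check: a rise from week 8 to week 10 would be visible, though its cause would not.

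A smaller wording problem concerns the same background treatment. Section 3.1 stops all antihistamines, whereas section 6.6 reads "Study participants will stop other first-generation antihistamines and start cetirizine (Zyrtec) 10 mg". A patient on another second-generation agent gets a different instruction from each section.

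**Working it through.** **Inputs.** 140 tablets, twice daily (7.1); start 14 days before first dose (6.6) or 7 days before week 0 (3.1); last visit at week 10, that is 70 days after week 0 (7.6); windows of ±5 days on Visits 2 to 7 (section 7). Visit 1 is day 0. The diary week is taken as the 7 days before a visit, which is an assumption.

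**The plan's figure.** 140 / 2 = 70 days, covering days 0 to 69. The number is reproduced exactly by weeks 0 to 10 without any lead-in (2 × 70 = 140), although dispensing is at Week -2.

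**Need and coverage at nominal visits, every dose taken.**

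| | 14-day lead-in (6.6) | 7-day lead-in (3.1) |
|---|---|---|
| Days needed | 14 + 70 = 84 | 7 + 70 = 77 |
| Tablets needed | 2 × 84 = 168 | 2 × 77 = 154 |
| Shortfall | 28 tablets, 14 days | 14 tablets, 7 days |
| Run-out, days after week 0 | 70 − 14 = 56 (week 8) | 70 − 7 = 63 (week 9) |
| Baseline diary week | days 7–13: 7 of 7 | days 0–6: 7 of 7 |
| Week-6 diary week | days 49–55: 7 of 7 | days 42–48: 7 of 7 |
| Week-8 diary week | days 63–69: 7 of 7 | days 56–62: 7 of 7 |
| Week-10 diary week | days 77–83: 0 of 7 | days 70–76: 0 of 7 |

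**Visit windows.** Visit 7 is counted from the actual Visit 2, and seven baseline diary days are required.

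- 14-day lead-in: Visit 7 falls between day 9 + 65 = 74 (diary days 67–73, 3 of 7 supplied) and day 19 + 75 = 94 (0 of 7).
- 7-day lead-in: between day 7 + 65 = 72 (diary days 65–71, 5 of 7) and day 12 + 75 = 87 (0 of 7).

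No timing in these windows supplies the whole week-10 week at full adherence.

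**Adherence, nominal visits.** If missed doses simply stretch the supply, the tablets reach week 10 only when no more than 140/168 = 83.3% (14-day) or 140/154 = 90.9% (7-day) of doses are taken.

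- At 95%: 140/1.9 = 73.7 days, giving 0 of 7 (14-day) or 73.7 − 70 = 3.7 of 7 (7-day).
- At 90%: 140/1.8 = 77.8 days, giving 77.8 − 77 = 0.8 of 7 (14-day) or 7 of 7 (7-day).

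**How far the week-8 check holds.** With Visit 6 five days late, its diary week is days 68–74 (2 of 7) under the 14-day lead-in or days 61–67 (7 of 7) under the 7-day one. With Visit 2 also five days late, it is days 73–79 (0 of 7) or days 66–72 (4 of 7). The latest Visit 5 is day 19 + 47 = 66 (diary days 59–65) or day 12 + 47 = 59 (days 52–58), so the week-6 week is always 7 of 7.

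**The case against.** The strongest reply is that this is a gap in the written supply plan, not evidence that cetirizine stops. Two sections tell patients to continue it, nothing forbids an unscheduled refill at one of the six later visits, and patients could buy it. All of that stands, and it is why the consequence is conditional.

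The visit lists and the schedule table also disagree elsewhere. The UCT is listed at Visit 1 in section 7.1 but marked at week 0 in the table, and adverse-event screening is marked at week 0 but missing from the Visit 2 list. Silence about a refill is therefore weaker evidence than it would be in a tidy protocol. On cetirizine, however, the lists and the table agree: Visit 1 only.

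The result also depends on adherence. Under the 7-day lead-in, about 90% adherence is enough to supply the whole week-10 week. Under the 14-day lead-in in section 6.6, the same adherence leaves less than one day supplied.

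Finally, patients are unresponsive to oral antihistamines by inclusion (section 5.1), the likely bias runs against the drug, and the study is exploratory. These points limit the weight of the concern. They do not reconcile 140 tablets with the stated duration.

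**Conclusion.** The concern holds, at minor severity. The dispensed quantity is 28 tablets (14 days) short of what section 6.6 requires, or 14 tablets (7 days) short under the lead-in in section 3.1. At nominal visits and full adherence, either lead-in leaves 0 of 7 week-10 diary days inside the supply, against 7 of 7 at baseline.

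The tablet arithmetic is firm. The coverage figures rest on the diary week being the 7 days before the visit and on no resupply. Any effect on UAS7 needs a patient to run out and not replace the tablets. Its size in UAS7 points cannot be derived from the documents. It is probably small and most likely understates improvement.

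**What to change.** Either of two changes closes the gap:

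- **Dispense more at Visit 1.** 168 tablets cover nominal visits, 178 a Visit 7 five days late (2 × 89), and 188 a late Visit 2 as well (2 × 94).
- **Keep 140 and add a refill of 48 tablets at Visit 5 (week 6)**, entered in both the visit list and the schedule table. Visit 5 is the last visit that always falls inside the 70-day supply: day 66 at the latest, against day 80 for Visit 6.

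The cost is 168 − 140 = 28 to 188 − 140 = 48 more tablets per patient, or 560 to 960 for 20 patients, and a few lines of wording. No new visit or assessment is needed.

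Secondary, and separable from the supply fix: state one antihistamine rule in sections 3.1 and 6.6 (which rule is for the sponsor-investigator to choose), and note any antihistamine change between weeks 0 and 10. The source-data list in section 4.5 has no item for this, so the note would need a line on the case report form.

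If supply lapsed for any patient, report the week-0 to week-8 UAS7 change descriptively beside the unchanged week-10 primary analysis, and exclude no one. Use week 6 where the week-8 diary week ran past the supply. The visit lists and schedule collect UAS7 at week 6, although section 3.1 says "UAS-7 and weekly ISS score will be calculated at week 0, 4, 8, and 10", so that sentence should be aligned with them.
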